5.1.3.2 Maintenance

One capsule of ponesimod or teriflunomide will be taken orally o.d., preferably in the morning, either with breakfast or before or after breakfast. It is preferable that the capsule be taken each day at approximately the same time. The capsule will be swallowed as a whole. The last administration date and time of study drug (capsule) prior to the study visits and the administration date and time of study drug (capsule) on the days of visits will be recorded in the eCRF.

On the day of the study visits, study drug must be administered only after the completion of the pre-dose safety assessments (diastolic blood pressure [DBP], systolic blood pressure [SBP], ECGs, PFTs, laboratory tests) and PK sampling (if scheduled).

5.1.4 Treatment assignment

A total of 1100 eligible subjects will be randomized in a 1:1 ratio to ponesimod 20 mg or teriflunomide 14 mg, stratified by prior use of MS disease-modifying treatment in the last two years prior to randomization (yes, no) and by baseline EDSS score (EDSS \leq 3.5, EDSS > 3.5).

Each of the study sites will be assigned a unique site number, and every subject will receive a unique screening number (= subject number), which identifies the subject throughout the study. After having confirmed the eligibility of the subject and prior to the start of study treatment, the investigator/delegate contacts the interactive response technology (IRT) at Visit 3 to randomize the subject. The IRT assigns a randomization number to the subject and assigns the treatment kit number, which matches the treatment arm assigned by the randomization list to the randomization number of each subject.

The randomization list is generated by an independent CRO (ALMAC Clinical technologies-see contact details in the IRT manual) and kept strictly confidential.

5.1.5 Blinding

5.1.5.1 Study drug material related blinding

This study will be performed in a double-blind fashion. The investigator and study staff, the subjects, the monitors, all Clinical Trial Team (CTT) members at Actelion and CROs involved in the conduct of the study will remain blinded to the treatment until study closure. Actelion staff responsible for clinical trial supply distribution will need to be unblinded to ensure adequate study oversight. These persons will be clearly identified, their unblinding will be documented in the trial master file and they will not take part in any CTT meeting after study set-up has been completed.

Until the time of unblinding for final data analysis, the randomization list is kept strictly confidential and accessible only to authorized persons who are not involved in the conduct of the study.

The investigational treatment and active comparator, and their respective matching placebos (if applicable, during the initial stage when the up-titration study drug treatments are administered in a double-dummy fashion) are indistinguishable, and all subject's kits will be packaged in the same way.

5.1.5.2 Functional blinding

First-dose effects on HR and AV conduction, lymphocyte counts reduction, and teriflunomide plasma concentration have been identified as potentially unblinding information. Access to this information by the site's staff and sponsor's study team will be restricted. The following measures will be taken to ensure that the efficacy assessments

(i.e., EDSS/FS) are done independently and that cardiac safety assessments, lymphocyte count and teriflunomide plasma concentration assessment are performed and reviewed without potential to introduce a bias:

- The primary endpoint (ARR) and the second key secondary endpoint (disability accumulation) are based on the evaluations of the EDSS and FSs, assessed by an efficacy assessor, not involved in any other aspects of patient care and management throughout the study.
- The subject will be instructed not to discuss AEs (other than those required for EDSS assessments), HR, pulmonary function and/or concomitant medications with the efficacy assessor.
- The principal investigator / treating neurologist and first-dose administrator evaluating • cardiac safety assessments must not discuss any issues related to patient care and management unless mandated for reasons of subject safety. On Day 1 and on the first day of re-initiation of study drug when post-dose monitoring is required, significant findings, which in view of the first-dose administrator meet the definition of an AE, have an onset after the study drug intake, and are resolved at the time of discharge of the subject, must be recorded directly on the AE page of the eCRF by the first-dose administrator/delegate. These AEs, the ECG interpretation reports and BP data collected on these days will not be visible to any of the blinded study personnel at the study site. At the sponsor's level, these events and ECGs and BP data will be entered into a separate eCRF and will only be visible to the site monitor and to the first-dose monitor. The site monitor will not reveal any potentially unblinding information to the rest of the site team or to the sponsor study team and will only discuss any of these data with the first-dose administrator or the first-dose monitor. The first-dose monitor is a role created by the sponsor for the purpose of keeping the rest of the sponsor's team blinded and assigned to (a) specific individual(s). The first-dose monitor will not reveal any potentially unblinding information to the site team or to the rest of the sponsor study team and her/his access to potentially unblinding information will be documented in the trial master file.
- Results of the total WBC count and total lymphocyte count will not be communicated to the sites, sponsor, and CRO unless one of the below applies:
 - A total lymphocyte count $< 0.2 \times 10^9$ /L is recorded by the central laboratory. In this event, an alert containing the total lymphocyte count result will be sent to the principal investigator and the sponsor. FU monitoring must be provided as described in Sections 5.1.13 and 7.3.14.

5 December 2018, page 92/376

- A WBC count > 20×10^9 /L or a lymphocyte count > 8.0×10^9 /L is recorded by the central laboratory [see Appendix 6]. In this event, an alert containing the total WBC or lymphocyte count result (as applicable) will be sent to the principal investigator and the sponsor.
- WBC and total lymphocyte counts measured at Visit 1 (Screening), 2 (Baseline), and any of the visits in the PTOP (if applicable) will be visible to the treating neurologist. Upon discontinuation of ponesimod, lymphocytes counts return to within normal ranges within one week. Lymphocytes counts are therefore expected to have returned to normal range during the 30 days safety follow up period preceding the start of PTOP.
- Teriflunomide plasma concentration will be assessed after study treatment discontinuation for women of childbearing potential and fertile male subjects not entering the extension study and willing to discontinue contraception [see Section 4.5]. Teriflunomide plasma concentration can also be assessed for any subjects not entering the extension study if deemed necessary for the subject's safety, at the investigator's discretion. The following rules will apply:
 - For subjects entering the AC-058B303 extension study, no teriflunomide plasma testing will be conducted as part of the AC-058B301 study. The timing of teriflunomide plasma concentration testing and procedures are described in the AC-058B303 study protocol (separate protocol).
 - For subjects not entering the AC-058B303 extension study, teriflunomide plasma concentration testing should not occur before:
 - 20 weeks after last drug intake, if the subject's compliance with the accelerated elimination procedure has been assessed as sufficient [see Section 5.1.14.2].
 - 35 weeks (i.e., 8 months) after last drug intake or EOS, whichever is last, if the subject's compliance with the accelerated elimination procedure has not been assessed as sufficient [see Sections 5.1.14.1 and 5.1.14.4].
 - In all cases, the results will not be communicated to the sponsor (except site monitor). Sites will receive the following notifications:
 - \circ if plasma concentration was < 0.02 mg/L: notification that the teriflunomide test was successfully performed

5 December 2018, page 93/376

- \circ if plasma concentration was ≥ 0.02 mg/L: full test results and notification that the subject should either repeat the accelerated elimination procedure [see Section 5.1.14] or wait an additional time period before another test may be performed.
- All MRI scans collected for the assessment of efficacy endpoints are evaluated by a central lab (MIAC) also in a fully blinded fashion.

Under no circumstances should potentially unblinding information be shared with the efficacy assessor.

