AE = adverse event; ALT = Alanine aminotransferase; AST = aspartate aminotransferase; CGI-C = Clinician's Global Impression of Change of patient's relapsing MS; CNS = central nervous system; DBP = diastolic blood pressure; DL_{CO} = diffusing capacity for the lungs measured using carbon monoxide; DIR = double inversion recovery; eC-SSRS = electronic self-rated version of the Columbia-Suicide Severity Rating Scale; ECG = electrocardiogram; eCRF = electronic case report form; EDSS = Expanded Disability Status Scale; EOS = End-of-Study; EOT = End-of-Treatment; FS = functional system; FSIQ-RMS = Fatigue Symptom and Impact Questionnaire-Relapsing Multiple Sclerosis; FU1 = follow-up visit 1; FU2 = follow-up visit 2; MRI = magnetic resonance imaging; MS = multiple sclerosis; MSFC = Multiple Sclerosis Functional Composite; MTR = magnetization transfer ratio; OCT = optical coherence tomography; PFT = pulmonary function test; PGI-S = Patient's Global Impression of Severity of Fatigue; PI = principal investigator; PK = pharmacokinetics; SAE = serious adverse event; SBP = systolic blood pressure; SDMT = Symbol Digit Modalities Test; WPAI:MS = Work Productivity and Activity Impairment Index: Multiple Sclerosis.

Periods	Name	POST-TREATMENT OBSERVATION PERIOD (PTOP) (to be performed after EOT) Up to 108 Weeks						
	Duration							
Visits	Number	6A, 8A, 9A, 11A,13A	7A, 12A	10A, 14A				
	Name	W12A, W36A, W48A, W72A, W96A	W24A, W84A	W60A, W108A				
	Time	Week 12-36-48- 72-96	Week 24 and 84	Week 60 and 108				
	Visit window	±7 days	±7 days	±7 days				
EDSS/ FS*		Х	Х	Х				
Relapse*(1)			X(1)<	>X(1)				
MRI*				Х				
FSIQ-RMS** (2), PGI-S**, CGI-C *		X (only Week12)	Х	Х				
Concomitant medications*		Х	Х	Х				
Physical examination*				Х				
Dermatological examination* (3)				Х				
SBP/DBP*		Х	Х	Х				
12-lead ECG **				Х				
Body temperature*		Х	Х	Х				
Pulmonary function tests** (4)				X (Week 108 only)				
Hematology/Chemistry** (fasted)			Х	Х				
Urinalysis*			Х	Х				
Pregnancy test*/** (5)		Х	Х	Х				
AEs/SAEs *		Х	Х	Х				

*Data collected in the eCRF

**Electronically transferred to sponsor.

Day 1 (date of randomization visit) is to be used as the reference date for the purpose of calculating the subsequent visit dates (and time windows). If the first PTOP visit windows overlaps with FU1 or FU2 visits, visits and assessments can be combined.

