1.3.2.2 Pharmacodynamics in humans

Oral administration of ponesimod dose-dependently reduces the circulating lymphocyte count in humans. The maximum reduction from baseline of approximately 65–80% is achieved after a single dose of \geq 50 mg, or 40 mg o.d. at steady state. The nadir in lymphocyte count is attained within 6–10 h following a given single dose. There is no evidence of tachyphylaxis on lymphocyte count. Peripheral blood counts of both T and B cells are reduced by ponesimod, while NK cells and neutrophils are not reduced. Food, race and gender do not appear to relevantly affect the PD of ponesimod. Upon discontinuation of ponesimod, the lymphocyte count generally returns to within the normal range within 1 week.

The magnitude of lymphocyte-count reductions seen with ponesimod in MS subjects was consistent with observations made after short-term treatment in healthy subjects. In the Phase 2 dose-finding study AC-058B201, at Week 24, the mean reductions from baseline in lymphocyte count were 49.8%, 65.3% and 68.6% in the ponesimod 10 mg, 20 mg, and 40 mg groups, respectively, compared to a mean increase of 3.3% in the placebo group. Lymphocyte counts remained stable on treatment and returned to baseline levels within 1 week following ponesimod treatment discontinuation.

More detailed information can be found in the IB [Ponesimod IB].

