3.1.3.1 Post-treatment safety follow-up period

All subjects will enter the safety FU period:

• For subjects who enter the extension study, the safety FU period lasts for 14–37 days after the last dose of study drug and includes a safety FU visit (FU1) 14–22 days after the last dose of study drug. If compliance to the teriflunomide accelerated elimination procedure is confirmed at FU1, the subjects will then be enrolled in the extension study. However, if compliance to the teriflunomide accelerated elimination procedure is not confirmed at FU1, the procedure may be repeated or missing intakes completed. In such cases an abbreviated FU2 will be conducted 23–37 days after the last dose of study drug. Provided sufficient compliance with the accelerated elimination procedure of teriflunomide [see Section 5.1.14.2] is documented, subjects will then be enrolled in the extension study.

Figure 1Subjects who enter the extension study

• For subjects who do not enter the extension study, the safety FU period lasts for 30 days after the last dose of study drug and includes two safety FU visits (FU1, FU2) at 14–22 and 30–37 days after the last dose of study drug, respectively.

Figure 2 Subjects who complete the 108-week treatment but do not enter the extension study

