3.1.3.2 Post-treatment observation period

Subjects who prematurely discontinue study treatment will enter the PTOP, which lasts from the last dose of study drug until 108 weeks after randomization (i.e., planned EOT period). The PTOP includes an abbreviated schedule of assessments at the time of the originally scheduled 12-weekly visits. The safety FU period lasts for 30 days after the last dose of study drug and includes two safety FU visits (FU1, FU2).

Figure 3 Subjects who prematurely discontinue study drug and enter the PTOP

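### Lymphocyte counts are unmasked at every PTOP visit partly because 30 days of follow-up are said to come first, but the PTOP starts at the last dose, so an early draw can show a still-reduced count

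*Protocol*

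**What the plan says.** Section 5.1.5.2 lists the fall in lymphocyte count among the data that could unblind. Total white-cell and lymphocyte results are withheld from sites, sponsor and CRO, apart from alert values and a few named visits. Those visits are screening, baseline, and "any of the visits in the PTOP (if applicable) will be visible to the treating neurologist".

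Two grounds are given for the PTOP exception:

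- Speed of recovery: "Upon discontinuation of ponesimod, lymphocytes counts return to within normal ranges within one week".
- Sequence of periods: counts are "expected to have returned to normal range during the 30 days safety follow up period preceding the start of PTOP".

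Other parts of the protocol describe the timing differently:

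- Section 3.1.3.2: subjects who stop early "will enter the PTOP, which lasts from the last dose of study drug until 108 weeks after randomization". The same section runs the 30-day safety follow-up from that same last dose.
- Table 3, note on visit dates: "If the first PTOP visit windows overlaps with FU1 or FU2 visits, visits and assessments can be combined". PTOP visits stay on the calendar counted from Day 1, within 7 days either way, and take place after EOT.
- Section 3.1.3.1, for subjects not entering the extension: the follow-up "includes two safety FU visits (FU1, FU2) at 14–22 and 30–37 days after the last dose of study drug, respectively".
- Section 1.3.2.2 states recovery less firmly: "the lymphocyte count generally returns to within the normal range within 1 week".

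Table 3 schedules hematology at four of the nine PTOP visits: Weeks 24, 60, 84 and 108.

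**The concern.** The release rule is attached to the name of the visit, while the protection it relies on is time since the last dose. If the PTOP begins at the last dose, the two can separate, and a count drawn within days of stopping is released because it belongs to a PTOP visit.

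The recipient matters. The treating neurologist already has the screening and baseline counts, so a fall is recognisable. Section 1.3.2.2 reports a mean reduction of 65.3% on ponesimod 20 mg at Week 24 of the Phase 2 study. Under Section 7.2.2 the treating neurologist (or principal investigator) decides whether symptoms are likely to be a relapse and refers the subject for EDSS. The treating neurologist then decides whether the relapse is confirmed. Relapse detection continues in the PTOP, and under Section 5.1.12 subjects who stop treatment remain in the study. The primary analysis in the synopsis is on the FAS with time in the study as offset, so I read relapses in the PTOP as counting.

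There is also a plain conflict of rules. FU1 and FU2 counts are withheld by default and PTOP counts are shown. A combined visit yields one sample, and the protocol does not say which rule governs it.

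**Working it through.** No sample size, power or alpha figure depends on this point, so there is no plan figure to reproduce. The check covers timing, residual drug and a rough count.

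**1. Order of the periods.** Section 5.1.5.2 places 30 days of follow-up before the PTOP. Section 3.1.3.2 starts both at the last dose. Table 3 foresees overlap between the first PTOP visit and FU1 or FU2. Section 3.1.4 ends the study at FU2 or the last PTOP visit, whichever is later, which also implies parallel periods. The sequence in 5.1.5.2 is therefore not guaranteed.

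**2. Earliest visible draw.** EOT is preferably 1 day and at most 7 days after the last dose (Section 3.1.2), and a PTOP visit only has to follow EOT. With a window of 7 days either way, a PTOP visit nominally due 0 to 13 days after the last dose can fall on about days 1 to 6.

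**3. Residual drug.** Section 1.3.2.1 gives a half-life of about 32 h and a good correlation between concentration and lymphocyte count. The fraction left after d days is 0.5^(24d/32):

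- day 1: 59%
- day 3: 21%
- day 5: 7%
- day 7: 2.6%
- day 14: 0.07%

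This agrees with recovery in about a week. It also shows that a draw in the first days may precede recovery.

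**4. Combined visits.** A PTOP visit nominally x days after the last dose has the window x−7 to x+7. It overlaps FU1 (days 14–22) for x from 7 to 29, and FU2 (days 30–37) for x from 23 to 44. A combined visit therefore falls no earlier than day 14 with FU1 or day 30 with FU2, at least a week beyond expected recovery.

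**5. How many subjects.** The synopsis assumes dropout of about 15% in year 1 and 7.5% in year 2.

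- Cumulative: 1 − 0.85 × 0.925 = 21.4%; 1100 × 0.214 ≈ 235.
- Study length: 108 × 7 = 756 days.
- With stops spread evenly, the share with a PTOP hematology visit nominally due within 7 days of the last dose, over four visits, is 4 × 7/756 = 28/756 = 3.7%, or 235 × 28/756 ≈ 8.7 subjects.
- Week 108 ends the PTOP, so a draw there leaves little later follow-up to influence. Over three visits: 21/756 = 2.8%; 235 × 21/756 ≈ 6.5 subjects.
- With equal discontinuation in the two arms, about half are on ponesimod: 6.5/2 ≈ 3.

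The count uses nominal dates. The visit window can move a draw earlier or later, and the requirement that the draw follow EOT removes some cases. Neither is modelled.

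**The case against.** The strongest reply is that 5.1.5.2 does not rest on the 30-day sequence alone. Its other ground is recovery within one week, and Section 1.3.2.2 supports it: in the Phase 2 study counts were back to baseline levels within a week of stopping. That stands. It limits any exposure to roughly the first week and to slow recoverers, whom the qualifier in Section 1.3.2.2 leaves possible.

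A reader might infer that combining a PTOP visit with FU1 or FU2 itself exposes suppressed counts. The documents do not support this: such visits fall at day 14 or later. Combining is mainly a conflict between two masking rules. One can also argue that the PTOP wording is simply an exception to the general rule and so governs a shared sample. That is a fair reading, but the protocol does not state it.

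The remaining route is narrow. EOT already includes hematology and is itself up to 7 days after the last dose, so a second draw must follow within the few days left. The text does not exclude it.

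The path to the primary endpoint is buffered. Confirmation needs a set EDSS/FS increase (Section 6.1.1), scored by a separate efficacy assessor who must not receive unblinding information and whose scores the treating neurologist may not alter. This reduces the scope for bias without removing it. Referral precedes EDSS at unscheduled visits, and whether the increase fits the symptoms remains the treating neurologist's judgement.

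Finally, a blanket 30-day mask would collide with Section 5.1.13.2, which requires at least weekly follow-up of low counts after a stop for that reason. This is correct, and the fix must allow for it.

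**Conclusion.** The contradiction is certain: one of the two grounds for releasing PTOP counts fails against Section 3.1.3.2 and Table 3. As written, a count drawn within about a week of the last dose can reach the person who screens and confirms relapses.

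The size is small: about 6 to 7 subjects with follow-up still to come, about 3 of them on ponesimod. This assumes evenly spread stops, equal discontinuation by arm, and that every planned dropout stops treatment but stays for the PTOP. Section 5.1.12 separates stopping treatment from leaving the study, so the number is lower if dropouts leave. It is higher if stops cluster just before scheduled visits.

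A reader might infer that every PTOP visit unblinds, or that the primary comparison is materially biased. Neither follows. Hematology is due at four of nine PTOP visits, most of these draws come after expected recovery, and EDSS/FS is scored separately. No sample size or error rate changes. The point is worth correcting because it is a specific gap in the blind that is cheap to close.

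**What to change.** - Reconcile Section 5.1.5.2 with Section 3.1.3.2 and the Table 3 note on when the PTOP starts and how it relates to the 30-day safety follow-up.
- In 5.1.5.2, tie routine release of white-cell and lymphocyte counts to time since the last dose instead of visit name. The 30 days that the section already presumes can serve. This is longer than the one-week recovery figure requires, but it is the plan's own premise and covers slow recoverers.
- State that a sample shared by FU1 or FU2 and a PTOP visit within that period stays masked, and which rule applies to a shared FU2 sample taken after it.
- Exempt the existing alerts in 5.1.5.2 and the follow-up of low counts required by Section 5.1.13.2, so that safety monitoring is unchanged.

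The cost is a few lines of text and a date-based release rule at the central laboratory. No visit, sample or analysis changes.

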Based on the interview and examination, the principal investigator / treating neurologist will determine if symptoms are likely to be due to a relapse (i.e., all elements from the relapse definition in Section 6.1.1 have been verified and, in the absence of another, better explanation of the subject's symptoms), the subject will be referred to the efficacy assessor for an EDSS assessment. (Note: At scheduled visits the EDSS assessment planned for this visit will be used). The completed questionnaire [see Appendix 12] and the outcome of the examination [see Appendix 13] will be collected in the eCRF.

Step 3: 'The efficacy assessor will perform the EDSS/FS assessment within 7 days from the onset of new or worsening neurological symptom(s) [see Section 7.2.1].

Ponesimod / ACT-128800 Relapsing multiple sclerosis Protocol AC-058B301, OPTIMUM Version 7 5 December 2018, page 126/376

Confidential

Important note: EDSS and FS assessments will be performed only by the efficacy assessor. The efficacy assessor must not consult prior EDSS/FS scores when performing the current EDSS/FS assessment. In no case will the treating neurologist alter the EDSS/FS score obtained by the efficacy assessor. If the relapse requires treatment with corticosteroids [see Section 5.2.3], treatment should be initiated as early as recommended by local clinical practice. The blinded neurological examination by the efficacy assessor must always be performed prior to the treatment start.

Step 4: The treating neurologist will review the EDSS/FS score obtained by the efficacy assessor and determine presence or absence of qualifying increase in EDSS/FS (i.e., an increase of the magnitude described in Section 6.1.1 from a previously clinically stable EDSS/FS score and consistent with the subject's new symptoms). Based on this review, the treating neurologist will decide if the relapse is confirmed or not, according to the protocol definition of confirmed relapse [see Section 6.1.1].

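### White-cell and lymphocyte counts are unmasked at PTOP visits on the premise of a prior 30-day follow-up that the protocol's own definitions contradict; the exposure is small

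*Protocol*

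**What the plan says.** Section 5.1.5.2 names the fall in lymphocyte count as potentially unblinding. Section 3.3.2 excludes white-cell and lymphocyte counts from the laboratory results that the treating neurologist handles.

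Section 5.1.5.2 then makes an exception. Counts from Screening, Baseline and "any of the visits in the PTOP (if applicable) will be visible to the treating neurologist". It gives two reasons. Counts recover within a week of stopping ponesimod, and "Lymphocytes counts are therefore expected to have returned to normal range during the 30 days safety follow up period preceding the start of PTOP".

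Other parts of the protocol describe the timing differently:
- Section 3.1.3.2: subjects who stop early enter PTOP, "which lasts from the last dose of study drug until 108 weeks after randomization". The same section adds: "The safety FU period lasts for 30 days after the last dose of study drug and includes two safety FU visits (FU1, FU2").
- Section 3.1.4: for these subjects, end of study is FU2 or the last PTOP visit, whichever is later. The last PTOP visit may therefore come before FU2.
- Table 3 note: visit dates are counted from Day 1, and "If the first PTOP visit windows overlaps with FU1 or FU2 visits, visits and assessments can be combined".

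On relapses, Section 7.2.2 has the treating neurologist interview the subject, judge whether a relapse is likely and refer for EDSS. After reviewing the scores, "the treating neurologist will decide if the relapse is confirmed or not, according to the protocol definition of confirmed relapse". Detection continues in PTOP.

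**The concern.** The release rule assumes an interval of 30 days between the last dose and PTOP. The protocol's definitions give an interval of zero. A subject who stops shortly before a scheduled PTOP haematology visit can have blood drawn while the ponesimod effect persists, and the rule as written shows that count to the treating neurologist. Baseline counts are visible too, so the comparison is direct. In the Phase 2 study the mean reduction on 20 mg at Week 24 was 65.3%, against a mean increase of 3.3% on placebo (Section 1.3.2.2).

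FU1 and FU2 counts are not on the release list, but a visit serving as both FU and PTOP falls under two rules. Section 5.1.5.2 does not say which one governs.

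The recipient is the person who decides whether symptoms are worked up as a relapse and whether the relapse is confirmed. Under Section 5.1.12 a subject in PTOP has not left the study, and the synopsis analyses relapse rate on all randomized subjects with time in the study as offset. On that reading, relapses in PTOP contribute to the primary endpoint.

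**Working it through.** No sample size, power or alpha figure is involved, and the protocol gives no figure to reproduce. The check compares the timing rules and then sizes the exposure.

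**Timing**
- Lag from last dose to start of PTOP: 30 days implied by Section 5.1.5.2, 0 days by Section 3.1.3.2.
- Earliest PTOP visit: the end-of-treatment (EOT) visit is 1 to 7 days after the last dose (Table 2 note), and PTOP visits follow EOT (Table 3). The shortest lag is 2 days.
- Example: last dose Day 165, EOT Day 166. The Week 24 PTOP visit is Day 168 ± 7, that is Days 161 to 175. It can take place on Day 167, 2 days after the last dose.
- With the 32-hour half-life of Section 1.3.2.1, 0.5^(48/32) = 35% of the plasma level remains at 2 days and 0.5^(168/32) = 3% at 7 days. The first week is where the count can be telling.

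**Share of early stoppers exposed**

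Assumptions: last-dose day uniform over Days 1 to 755; haematology at Weeks 24, 60, 84 and 108 (Days 168, 420, 588, 756), as Table 3 appears to show; EOT 1 day after the last dose, so lags run from 2 days.

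Share = (visits × qualifying lag days) / 755.

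| Lag from last dose | Qualifying days per visit | Share |
|---|---|---|
| under 7 days | 5 (lags 2–6) | 4 × 5 / 755 = 2.6% |
| under 14 days | 12 (lags 2–13) | 4 × 12 / 755 = 6.4% |
| under 30 days | 28 (lags 2–29) | 4 × 28 / 755 = 14.8% |

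If every visit is at the late edge of its window (+7 days), the shares are 2.0%, 5.6% and 14.0%.

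**Number of ponesimod subjects**

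The synopsis assumes dropout of 15% in year 1 and 7.5% in year 2. Using this as a proxy for treatment discontinuation: 1 − 0.85 × 0.925 = 21.4%, and 550 × 0.21375 = 117.6 subjects.
- under 7 days: 117.6 × 0.0265 = 3.1
- under 14 days: 117.6 × 0.0636 = 7.5
- under 30 days: 117.6 × 0.1483 = 17.4

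**Sensitivity**
- Without Week 108, after which almost no relapse decision remains: 3 × 5 / 755 = 2.0%, about 2 subjects under 7 days.
- If every EOT visit were 7 days after the last dose, the shortest lag would be 8 days. None would then fall under 7 days, and 4 × 6 / 755 = 3.2%, about 4 subjects, under 14 days.

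**The case against.** **Recovery within a week.** This reason for release does not depend on the 30-day sentence, and Section 1.3.2.2 supports it. It stands, and it covers most PTOP visits more than about 7 days after the last dose. Section 1.3.2.2 states recovery only as the general pattern, so slow recoverers remain as a tail.

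**The blinded assessor.** A confirmed relapse needs a qualifying EDSS/FS increase (Section 6.1.1). It is scored by an efficacy assessor who sees no laboratory results (Section 3.3.3), and the neurologist may not alter the score (Section 7.2.2). This also stands. A reader might infer that the neurologist could confirm relapses from knowledge of the arm, or that the relapse-rate comparison is materially biased. The documents support neither. What stays open is the decision to refer and the judgement that the score change fits the symptoms.

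**Combined visits.** No text seen says that a combined visit releases its count; this is inferred from the release list. Sections 7.3.14.2, 8.3.2 and 11 were not in the text available and could bear on it. Even so, Section 5.1.5.2 should not rest on a sequence that Section 3.1.3.2 denies.

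**Teriflunomide results.** A reader might extend the point to these. A level of 0.02 mg/L or more is sent to the site as "full test results and notification that the subject should either repeat the accelerated elimination procedure" or wait for a later test, possibly while the subject is still in PTOP. The extension does not hold as a masking defect. Testing is optional. For compliant subjects the protocol anticipates a level below the limit and then withholds the value. Full disclosure of an unexpected level is a deliberate safety trade-off. Sending it to another physician would protect little, because the treating neurologist manages care and contraception counselling (Section 3.3.2) and would learn of it anyway. Only the notification wording is inconsistent.

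**Conclusion.** The contradiction is established from the text: Section 5.1.5.2 relies on a 30-day interval before PTOP that Sections 3.1.3.2 and 3.1.4 and the Table 3 note rule out. As written, the rule can show the physician who refers and confirms relapses a count that the protocol itself treats as unblinding.

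The practical size is small: about 3 ponesimod subjects with a PTOP haematology visit less than 7 days after the last dose and about 7 less than 14 days after, out of about 550. These counts are illustrative. They rest on uniform stopping times, EOT one day after the last dose, and dropout rates as a proxy for discontinuation. The protocol states no discontinuation rate, and subjects who leave the study altogether have no later PTOP visits (Section 5.1.12). An effect on the primary endpoint is possible through the referral and consistency judgements but is not shown. The point merits correction because the remedy is cheap, not because the trial's conclusion is at risk.

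**What to change.** Reconcile Section 5.1.5.2 with Sections 3.1.3.2 and 3.1.4 and Table 3:
1. Remove the statement that a 30-day follow-up precedes PTOP.
2. Release white-cell and lymphocyte counts to the treating neurologist only from PTOP visits more than 30 days after the last dose and after FU2.
3. State that counts from a combined FU/PTOP visit stay masked.
4. Leave the existing alert limits, and the follow-up of alerted subjects, unchanged.

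Separately, reconcile the teriflunomide notification wording. For a level below 0.02 mg/L, Section 5.1.5.2 reports only that the test was performed, while Section 5.1.14.4 also reports that the level is below the limit. For a high level, Section 5.1.5.2 uses 0.02 mg/L or more, while Section 5.1.14.4 opens with more than 0.02 mg/L.

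Cost: one date rule in central laboratory reporting, which needs the last-dose date, and no new staff. Routine counts become visible to the neurologist up to 30 days later than now. A count drawn inside that window should stay withheld, since later release would be just as informative. For those subjects, about 15% of early stoppers on the assumptions above, the first visible routine count is then the next PTOP one, if any. Safety alerts still reach the site.
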